7.4.3 Exploratory analysis

The exploratory analysis is to evaluate the impact of the baseline host and virological characteristics (viral titer, mutation patterns, etc.) and early HBV DNA suppression on response to TDF at week 144. Multiple-factor logistic regression analysis will be used to assess the baseline variables that were significantly associated with HBV DNA negativity at week 144. The factors includeHBV DNA level, resistance type, HBeAg status, prior treatment with ADV, prior treatment with ETV, overall duration of prior NA treatment, compliance, cirrhosis, ALT level, age, gender, BMI, AST, r-GT, platelets, INR, total bilirubin, albumin, etc. The OR and 95% CI of each factor will be provided in the table.

Time to virological response to TDF defined as HBV DNA <20 IU/mL, as a time-to-event variable, will be analyzed by Kaplan-Meier curve for overall and subjects with different patterns of mutation. Log-rank test will be performed separately for each of the following factors: HBV DNA level, HBeAg status, prior treatment with ADV, resistance type (ADV or not), cirrhosis, compliance and

patterns of mutation. Cox regression model will be conducted to include all above factors and additional factors: prior treatment with IFN, ALT level, age, and gender.

In addition, three listings will be provided for

- The ALT for patients with any HBeAg Loss, HBeAg Seroconversion, HBsAg Loss and HBsAg Seroconversion over time
- The relationship between HBV DNA and medical history for previously exposed to NAs >6 months
- The HBV DNA for patients with virological breakthrough (defined as 1 log increase in HBV DNA from nadir determined by two sequential HBV DNA measurements), and
- The HBV DNA for patients with unsatisfactory response (defined as subjects who have HBV DNA ≥200 IU/mL at week 48 and afterwards have ≤ 1 log10 IU/mL decrease in HBV DNA at two consecutive tests, confirmed by a third visit (additional visit) at least one month apart).

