3.2 Sample size

Sample sizes are chosen based on feasibility and precision because no hypothesis is tested in this study. The primary endpoint is the proportion of subjects with serum HBV DNA <20 IU/mL of TDF in multiple NAs treatment failure patients at Week 144.

To decide the number of subjects for analysis, some precision calculations have been performed. From our historical data, we hypothesize that the proportion of subjects with serum HBV DNA <20 IU/mL in multiple NAs treatment failure patients treated with TDF at Week 144 was 80%. A sample size of 170 patients will allow us to estimate the confidence interval of the incidence with a margin of error at 6% (range from 74-86%). Assuming a dropout rate of 15 per cent during a 144 week period, the number of patients required overall is estimated to be 200.

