6.2 Data handling

Missing data can have an impact upon the interpretation of the trial data. In general, values for missing data will not be imputed unless otherwise specified.

All serum HBV DNA results below the lower limit of detection (<20 IU/mL) or results of "not detected" will be analyzed as being the value of the lower limit of quantification, which is 20 IU/mL. For the primary endpoint analyses and other analyses of response (success, failure) at a particular time point, a discontinued subject was considered as "failure" for all efficacy responses post termination. And the missing values of categorical efficacy endpoints (success, failure) will be imputed as "failure" at the analysis visits.

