7.4.1 Analysis of primary variable

The primary efficacy endpoint for this study is the proportion of subjects with serum HBV DNA <20 IU/mL at week 144. Primary efficacy endpoints are evaluated by count and percentage, and two-sided 95% CI will also be provided based on normal approximation and continuity correction.

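### The week-144 predictor model inherits the rule that dropouts are failures, so it mixes retention with virological response, and no companion model separates the two.

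*SAP*

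**What the plan says.** SAP 2.2 and protocol 2.2 list the effect of baseline characteristics and early suppression on response to TDF among the secondary objectives. SAP 5.3 carries it as an exploratory endpoint. The analysis is in SAP 7.4.3: "Multiple-factor logistic regression analysis will be used to assess the baseline variables that were significantly associated with HBV DNA negativity at week 144". Eighteen factors are named, followed by an open-ended etc. The results go to Table 4.9.1 (mITT) and Table 4.9.2 (PP).

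SAP 7.4.3 does not say how a subject without a week-144 value enters the model. SAP 6.2 does. For the primary endpoint and "other analyses of response (success, failure) at a particular time point, a discontinued subject was considered as" a failure at all time points after leaving. The next sentence of SAP 6.2 also imputes missing categorical efficacy responses as failure. HBV DNA negativity at week 144 is a success/failure response at a particular time point, so the model falls under the rule.

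Protocol 8.3.5 limits its rule for non-completers to the primary analysis, and protocol 8.3.5.1 plans the multiple-factor analysis without one. The extension to the predictor model is therefore made in the SAP. Neither document plans an observed-case or imputed version.

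**The concern.** For a single response proportion, counting dropouts as failures is conservative and easy to interpret. In a regression it does something else. The dependent variable becomes stayed in the study and was suppressed, so each coefficient blends an effect on the virus with an effect on staying in the study.

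Several of the discontinuation reasons in SAP 7.1 say nothing about viral response: voluntary withdrawal, loss to follow-up, pregnancy, and treatment interruption of 28 days or more. Age, gender and compliance are among the named factors and could plausibly relate to such reasons. Subjects with an unsatisfactory virological response may receive add-on therapy within the study (protocol 3.1), so a virological failure need not become a dropout.

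At stake is how the table will be read. Its title presents it as the relationship between baseline variables and virological response, and protocol 1.2 gives the uncertain effect of adefovir resistance as a reason for the study. A resistance effect could look smaller than it is, and a retention effect could be reported as a response effect.

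**Working it through.** **Inputs from the plan (SAP 3.2; protocol 4.1 and 8.2.1).** The assumed proportion below 20 IU/mL among patients "treated with TDF at Week 144 was 80"%. On precision: "A sample size of 170 patients will allow us to estimate the confidence interval of the incidence with a margin of error at 6"%. On enrolment: "Assuming a dropout rate of 15 per cent during a 144 week period, the number of patients required overall is estimated to be 200". SAP 7.4.1 gives a two-sided 95% interval, so z = 1.96.

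**The plan's own figures.** N = p(1−p)(z/e)² = 0.80 × 0.20 × (1.96/0.06)² = 170.7, against 170 stated. The margin at n = 170 is 1.96 × √(0.16/170) = 6.01%. Enrolment is 170/0.85 = 200, so 30 dropouts are expected. The figures reproduce.

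**Make-up of the scored failures.**

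- Base case: the 80% is a completer rate. Protocol 4.1 labels the 170 as completed/evaluable, and the inflation to 200 comes afterwards. Virological failures: 0.20 × 170 = 34. Scored failures: 34 + 30 = 64. Dropout share: 30/64 = 47%.
- Sensitivity case: the 80% already counts dropouts as failures. Scored failures: 0.20 × 200 = 40, of which 10 are virological. Dropout share: 30/40 = 75%. This implies 160/170 = 94% response among completers.
- With 10% dropout instead of 15%, the shares are 20/56 = 36% and 20/40 = 50%.

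**Wrong labels.** Not every dropout is a responder. If dropouts would have failed at the completers' 20%, 0.80 × 30 = 24 are mislabelled, which is 24/64 = 38% of scored failures in the base case.

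**Effect on odds ratios.** The scored failure risk is d + (1−d)f, where d is the dropout risk and f the virological failure risk. The factor's prevalence (20%), its true odds ratio and its dropout risks are assumptions; the plan gives none.

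1. Factor unrelated to dropout, true odds ratio 3, d = 0.15 in both groups.
   - Base case: f = 36.3% vs 15.9%. Scored risks are 0.15 + 0.85 × 0.363 = 45.8% and 0.15 + 0.85 × 0.159 = 28.5%. Odds ratio 2.1.
   - Sensitivity case: f = 12.0% vs 4.4%. Scored risks are 25.2% and 18.7%. Odds ratio 1.5.
2. Factor with no virological effect, dropout 27% vs 12% (0.2 × 27% + 0.8 × 12% = 15%).
   - Base case: 0.27 + 0.73 × 0.20 = 41.6% and 0.12 + 0.88 × 0.20 = 29.6%. Odds ratio 1.7.
   - Sensitivity case (f = 10/170 = 5.9%): 31.3% and 17.2%. Odds ratio 2.2.
3. Factor with both effects (virological odds ratio 3, dropout 27% vs 12%).
   - Base case: 53.5% vs 26.0%. Odds ratio 3.3.
   - Sensitivity case: 35.8% vs 15.8%. Odds ratio 3.0. There is no material shrinkage.

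The pattern does not depend on 20% prevalence. At 50%, a true odds ratio of 3 unrelated to dropout becomes 1.94 (base) or 1.35 (sensitivity), and a dropout-only odds ratio of 3 appears as 1.63 or 2.22.

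In simulations of 200 subjects with a single-factor Wald test, the dropout-only factor in item 2 reaches p < 0.05 in about 31% of trials (base) or 50% (sensitivity). On observed values the figure is 3% to 4%. These rates illustrate the mechanism and do not describe the planned multi-factor model.

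**The case against.** The strongest defence is that using one definition of response for the primary proportion and for its predictors is coherent. It gives a composite, response with retention, in an analysis labelled exploratory, in a study that tests no hypothesis. That stands as a reason to keep the model. It does not support reading the output as predictors of virological response.

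A second objection is that an observed-case model is not a clean replacement. It selects on a post-baseline event and is biased if dropout is informative. It also leaves 34 failures for 18 named factors (34/18 = 1.9 per factor), against 64/18 = 3.6 under the planned rule. This stands too, and it is why the remedy adds a model rather than replacing one.

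Four stronger readings are tempting, and the documents do not support them.

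- Most failures are mislabelled. The 75% figure is a share of dropouts, not of wrong labels, and it depends on the less natural reading of the 80%. SAP 7.1 also lists lack of efficacy and adverse events among the reasons for leaving.
- All true predictors shrink. Item 3 shows that this fails when a factor drives both outcomes in the same direction.
- The per-protocol table has the same problem to the same degree. SAP 7.1 leaves PP exclusions to the study team before database lock and does not name dropout or a missing week-144 value as a category. The effect there is undetermined.
- The Cox model treats the same subjects in the opposite way. SAP 7.4.3 says "Time to virological response to TDF defined as HBV DNA <20 IU/mL, as a time-to-event variable, will be analyzed by Kaplan-Meier curve", but no censoring rule is given, and time to first response is a different endpoint from status at week 144. No contradiction can be shown.

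**Conclusion.** The concern holds for the mITT predictor model, and for the PP model only so far as dropouts remain in that set. As written, the SAP carries the failure rule into a regression meant to explain response to TDF, with nothing beside it to separate virological from retention effects.

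The 47% share is the best reading of the plan's figures and 75% is an upper sensitivity value; both depend on the planned 15% dropout and 80% response. The odds-ratio results rest on the assumed prevalence, effect size and dropout contrast. Confidence is high that the rule reaches this model, and lower for the size of the effect. The primary proportion is not affected, and the failure rule is defensible there.

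**What to change.** In SAP 7.4.3:

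- State that the model under the SAP 6.2 rule describes response with retention.
- Pre-specify beside it a model of virological response, with week-144 HBV DNA multiply imputed from the 12-weekly central-laboratory series, or fitted on observed week-144 values.
- Tabulate dropout and its reasons by the same factors.
- Describe a factor as a predictor of virological response to TDF only where the models agree.

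The cost is SAP wording, one or two extra model runs and one table, with no new data. The added model needs a missing-at-random assumption. With about 34 failures, an observed-case fit also needs a shorter factor list or penalised estimates, chosen in advance.

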#### 8.3.5.1. Efficacy analyses

In this study, data will be summarised as mean, medium, standard deviation, maximum, and minimum for continuous variables, and in tables of frequencies and percentages for categorical variables.

For the primary endpoint, descriptive analysis will be used to evaluate the efficacy of TDF in multiple NAs treatment failure patients.

Multiple-factor analysis will be used to assess the baseline variables that were significantly associated with HBV DNA negativity at week 144.

The detail of primary, secondary and other efficacy endpoint analysis will be included in the RAP.

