4. ANALYSIS SET

• Modified Intent-to-treat (mITT) Population

The mITT population is defined as all recruited subjects who receive at least one dose of study medication.

• Per Protocol (PP) population

The PP population will consist of subjects in the mITT population who have no major protocol deviations that impact the safety and efficacy evaluation.

• Safety Analysis (SA) population

The SA population is defined as all subjects who receive at least one dose of study medication and have at least one post baseline safety assessment.

All efficacy endpoints will be analyzed using the mITT and PP population. All safety endpoints will be analyzed using the SA population according to the actual treatment they received.

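### The week-144 logistic model carries 18 or more factors on about 40–64 non-responders: odds ratios would be inflated under ordinary maximum likelihood, and, as a separate matter, the number of tests makes a false predictor likely.

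*SAP*

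**What the plan says.** SAP 7.4.3 describes a single multiple-factor logistic regression for HBV DNA negativity at week 144. The factors are HBV DNA level, resistance type, HBeAg status, prior ADV and prior ETV, followed by "overall duration of prior NA treatment, compliance, cirrhosis, ALT level, age, gender, BMI, AST, r-GT, platelets, INR, total bilirubin, albumin, etc". An odds ratio with 95% CI is promised for each factor. Tables 4.9.1 and 4.9.2 report the analysis for mITT and PP.

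Protocol 8.3.5.1 gives the purpose: "Multiple-factor analysis will be used to assess the baseline variables that were significantly associated with HBV DNA negativity at week 144". SAP 7.4.3 repeats it.

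Neither document states, for this model, an estimation method beyond logistic regression, an entry or selection rule, a significance level, a multiplicity rule, or what happens if the fit fails to converge. The multiplicity sentence in SAP 3.1 concerns only the analyses at different data cuts.

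The size of the data follows from three statements:
- SAP 3.2 assumes that the response proportion in patients "treated with TDF at Week 144 was 80"%, and adds: "Assuming a dropout rate of 15 per cent during a 144 week period, the number of patients required overall is estimated to be 200".
- SAP 6.2 counts discontinued subjects as failures, and "missing values of categorical efficacy endpoints (success, failure) will be imputed as" failure.
- SAP 4 sets the main population: "The mITT population is defined as all recruited subjects who receive at least one dose of study medication".

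**The concern.** In a logistic model the information is limited by the rarer outcome, here non-response. With few non-responders per parameter, ordinary maximum likelihood pushes odds ratios away from 1 and some fits separate. Independently of that, testing many factors and picking out the significant ones gives many chances of a false finding.

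The question matters to this study. Protocol 1.2 notes that two small studies disagreed on whether ADV resistance weakens the response to TDF, and says the data could help optimise how TDF is used. The impact of baseline characteristics and early HBV DNA suppression is listed as a secondary objective in Protocol 2.2 and SAP 2.2, although the matching endpoint is labelled exploratory. An overfitted model read for significance could add another unreliable answer.

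**Working it through.** **1. Reproduce the plan's figures.** SAP 3.2 says "A sample size of 170 patients will allow us to estimate the confidence interval of the incidence with a margin of error at" 6%. With N = p(1−p)(z/e)², p = 0.80, z = 1.96 and e = 0.06, N = 0.16 × (1.96/0.06)² = 170.7, against 170 stated. For dropout, 170/0.85 = 200, as stated.

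**2. Non-responders.**
- 80% applied to all 200: 200 × 0.20 = 40.
- 80% applied to 170, with the 30 dropouts counted as failures: 200 − 0.80 × 170 = 64 (response 68%).
- PP, assuming 170 subjects: 170 × 0.20 = 34.

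**3. Parameters.** Eighteen factors are named. SAP 5.3 also lists prior IFN and early HBV DNA suppression, giving 20. If resistance type uses the four-level grouping in SAP 7.4.2, it takes 3 degrees of freedom instead of 1, giving about 22.

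**4. Events per parameter.**

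| Non-responders | 18 parameters | 22 parameters |
|---|---|---|
| 40 | 2.2 | 1.8 |
| 64 | 3.6 | 2.9 |
| 34 (PP, assumed) | 1.9 | 1.5 |

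**5. Sparse-data bias.** The simulations used n = 200, 18 or 19 parameters and event rates of 20% and 32%. The covariate distributions, correlations and true effects are assumptions.
- Ordinary maximum likelihood: log odds ratios averaged 1.11–1.19 times the truth. A true OR of 2.0 then reads exp(1.11 × 0.693) = 2.16 to exp(1.19 × 0.693) = 2.28.
- With 34 non-responders in 170, the ratio was 1.16–1.23.
- Among factors reaching p < 0.05 at n = 200, the ratio averaged 1.38–1.53. These are the ones a reading by significance would highlight.
- Up to about 4% of fits with 40 non-responders, and 6% with 34, did not converge or separated.
- Firth's method with the same factors: inflation of about 0–4%.

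**6. Multiplicity.** For k independent null factors each tested at 0.05, the chance of at least one false flag is 1 − 0.95^k.

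| Null factors k | 6 | 8 | 13 | 14 | 15 | 17 | 18 |
|---|---|---|---|---|---|---|---|
| Chance | 26% | 34% | 48.7% | 51.2% | 53.7% | 58% | 60.3% |

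Simulated maximum likelihood at n = 200 gave 55–58% with 15 null factors and 62–65% with 17 or 18. The per-test error was about 5.7–5.9%, only slightly above nominal.

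**7. Separating the two problems.** At n = 3000 (600–960 events) the inflation was 0–1%, yet at least one null factor was still flagged in 52–64% of runs. At n = 200, Firth's method removed most of the inflation but still flagged at least one null factor in 42–51% of runs. Part of that drop is conservatism: in one set of runs the Firth–Wald per-test error was 4.1% and power fell by 3–7 points.

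**The case against.** The strongest case against is that nothing hangs on this model. It is exploratory in Protocol and SAP alike, Protocol 8.1 says no hypothesis is tested, and the primary proportion does not use it. An inflation of 11–19% on the log scale is modest beside the interval width to be expected from 40–64 events. The SAP does not say that all factors are entered together, that estimation is by unpenalised maximum likelihood, or that 0.05 is the threshold. The table shells are in a separate document, so part of the planned fit is inferred.

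Most of this stands and limits the severity. It does not remove the point. The question is also a stated secondary objective, both documents speak of significant association, and the SAP's silence on how the model is fitted and read is itself the gap.

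A reader might infer that the small event count is what makes a false predictor likely. The working does not support that: with ample events the chance is about the same. Nor is a false flag more likely than not in every case. Under independence that needs about 14 or more truly null factors; with 13 the chance is 48.7%.

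**Conclusion.** The point holds as two separate problems.

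1. **Sparse-data bias.** With 2–4 non-responders per parameter (slightly fewer in PP or with 22 parameters), log odds ratios would be inflated by about 11–19% if the model is fitted by ordinary maximum likelihood. The size rests on assumed covariates and effects.
2. **Multiplicity.** The chance of at least one false significant factor is about 55–65%, provided that all factors are entered together, most are truly null and each is tested at 0.05. The documents state none of these conditions; they are inferred from the promise of an OR and 95% CI for each factor and from the reference to significance. Changing the estimator does not cure this.

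It would be wrong to conclude that the week-144 primary result is compromised; only the reported predictors are affected. Severity is low to moderate, and the change is a cheap improvement.

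**What to change.** Before database lock:

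- In SAP 7.4.3, state that the listed model is fitted by Firth's penalised likelihood with profile-likelihood 95% CIs. Close the factor list and state how resistance type is coded.
- State that p-values are nominal and hypothesis-generating, and that predictors are not selected by significance. SAP 7.4.2 already calls its mutation-pattern p-values nominal. The wording on significant association also stands in Protocol 8.3.5.1, so align both documents. ORs with CIs are already planned and stay.
- Optionally, name a short main model on the questions the protocol itself raises (viral titre, mutation pattern, early HBV DNA suppression), with the other factors as supportive. Early suppression is measured after baseline and is not defined in the SAP, so its time point and cut-off would need stating. With 6–8 parameters there would be 5 (40/8) to about 11 (64/6) events per parameter. If all 6–8 terms were null, the false-flag chance would still be 26–34%, so the nominal reading of p-values is needed here too.

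Cost: one fitting option and some wording in two documents, with no new data. The downsides are slightly conservative tests with a small loss of power and, if the short model is adopted, fewer headline predictors.

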resistance did not influence the antiviral efficacy of TDF, the presence of ADV resistance impaired TDF efficacy (100% versus 52% probability of HBV DNA <400 copies/ml, respectively). The apparent discrepancy between two studies may be explained by the different baseline HBV DNA titre. The mean baseline HBV DNA viral load in van Bommel's study was much higher compared to the baseline HBV DNA in the Patterson study (>8.0 log10 copies/mL and 6.0 log10 copies/ml, respectively). Due to the fact that both studies had relatively small numbers of patients, it is still yet to be determined how ADV-R impacts response rates to TDF.

Our phase IV study is a multi-centre, prospective study and is expected to enrol a number of subjects(up to 20%) with confirmed multi-drug resistance (although the exact proportion of total subjects is unknown). The purpose of our study is to evaluate the efficacy of TDF treatment in Chinese CHB patients following failure of multiple NAs. In addition, we will also explore the relationship of baseline factors and early HBV DNA suppression to long-term virological response. The efficacy of TDF in multi-drug resistant patients will be analysed separately. The data generated by this study could then be used to optimize the clinical application of TDF and provide new evidence for management of the HBV infections following failure of multiple NAs.

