# 8. DATA ANALYSIS AND STATISTICAL CONSIDERATIONS

## 8.1. Hypotheses

No hypothesis is tested in this study.

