3. STUDY DESIGN

3.1 Overall study design

This is a single-arm, open-label, multi-centre study to assess the efficacy of TDF in CHB patients following failure of multiple NAs.

The study will enroll 200 CHB patients following failure of multiple NAs. All the eligible study subjects will undergo safety and efficacy assessments every 12 weeks for a total of 14 visits.

Screen phase (Visit 1): About 230 subjects will be assessed for eligibility at a screening visit, with eligible patients returning for a baseline assessment after approximately 4 weeks. Multiple NAs treatment failure is defined as HBV DNA higher than 200 IU/mL after two or more different NA(s) treatments (i.e. initiate with mono-therapy followed by add-on/switch rescue therapy; at least 6 months continuous treatment for each regimen, total duration to be no less than 12 months). At visit 1 all the testing will be performed locally except for the HBV DNA quantification which will be measured by a central lab. The subjects will maintain their current treatment from screening visit to baseline visit. All subjects will provide written informed consent before screening.

Treatment phase (Visits 2 to 14): In the 144 weeks open label period, all enrolled subjects will receive open label TDF at a dose of 300mg orally once daily. At each visit, subjects will be questioned about adverse events, concurrent medications, and study drug accountability; take chemistry (liver function, blood glucose, creatine phosphokinase) test; take electrolytes (sodium, potassium, chloridum, phosphorus and calcium) test; take pregnancy test; take urinalysis test; take renal function (blood creatinine clearance, bloodurea nitrogen and blood uric acid) test. Blood routine and International Normalized Ratio(INR) and HBV markers will be measured every 24 weeks. Abdominal ultrasound and serum alpha-fetoprotein test will be tested every 24 weeks. Serum samples will be collected and analyzed for HBV DNA levels in a central lab from visit 2 to 14. At the visit 2, resistance surveillance of the HBV polymerase gene will be performed by direct sequencing for all subjects at baseline.

No formal interim analysis was planned. Key analysis outputs will be provided annually with the 48-week and 96-week cutoff data for publication purpose. No adjustment for multiplicity will be made for the analysis in different period.

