5.3 Exploratory endpoints

- Evaluate the impact of the baseline host and virological characteristics (HBV DNA level, resistance type, HBeAg status, prior treatment with ADV, prior treatment with ETV, prior treatment with IFN, overall duration of prior NA treatment, compliance, cirrhosis, ALT level, age, gender, BMI, AST, r-GT, platelets, INR, total bilirubin, albumin, etc.) and early HBV DNA suppression on response to TDF at week 144.
- Time to virological response to TDF (defined as HBV DNA <20 IU/mL) for overall and subjects with different patterns of mutation.

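### SAP 7.4.3 states no cut-point or functional form for baseline HBV DNA level; a two-group log-rank test would cost the univariable analysis roughly a quarter to a half of its information

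*SAP*

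**What the plan says.** SAP 5.3 names baseline HBV DNA among the characteristics to be explored ("HBV DNA level, resistance type, HBeAg status, prior treatment with ADV" and others) and gives no categories.

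SAP 7.4.3 uses it in three places:

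- **Logistic model.** It is one of the factors for response at week 144.
- **Univariable log-rank test.** The outcome is "Time to virological response to TDF defined as HBV DNA <20 IU/mL, as a time-to-event variable". The sentence reads "Log-rank test will be performed separately for each of the following factors: HBV DNA level, HBeAg status", and the list continues to "resistance type (ADV or not), cirrhosis, compliance and" mutation patterns. Resistance type is given its two groups in that list. HBV DNA level is not.
- **Cox model.** "Cox regression model will be conducted to include all above factors and additional factors: prior treatment with IFN, ALT level, age, and gender". This brings HBV DNA level in again.

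No number of groups, cut-point, selection rule or statement of continuous form appears for HBV DNA level in either document. Protocol 8.1 states "No hypothesis is tested in this study", and SAP 7.4.3 is headed as exploratory. No alpha is set for the log-rank tests. SAP 9 says that the mock tables are in a separate document, which is not available here.

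**The concern.** Taken as an ordinary log-rank test, the plan needs HBV DNA level in classes that nobody has defined. Two things follow.

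- Grouping a continuous predictor discards information, even when the cut is fixed in advance.
- An unfixed cut can be chosen with outcomes in view. The study is open-label, and SAP 3.1 says "Key analysis outputs will be provided annually with the 48-week and 96-week cutoff data for publication purpose". The annual outputs include an individual HBV DNA listing (Listing 4.1) and HBV DNA distributions over time (Figure 4.5.3).

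The factor is of real interest. Viral titer is named in the objective on baseline characteristics. Protocol 1.2 says of the two earlier TDF studies that disagree on adefovir resistance: "The apparent discrepancy between two studies may be explained by the different baseline HBV DNA titre". The log-rank results have their own tables (4.11.1 and 4.11.2) and, unlike the mutation-pattern comparisons in SAP 7.4.2, their p-values are not labelled nominal. No Kaplan-Meier figure by HBV DNA level is listed, so grouping would serve only the test.

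**Working it through.** **Inputs from the documents.** 80% response at week 144, 170 evaluable, 15% dropout, 200 enrolled (Protocol 8.2.1, SAP 3.2); visits every 12 weeks to week 144 (SAP 3.1).

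**The plan's own figures.** N = p(1−p)(z/e)² = 0.8 × 0.2 × (1.96/0.06)² = 170.7, stated as 170. Then 170/0.85 = 200. All nine rows of Protocol Table 2 also reproduce. The documents give no figure for the log-rank test.

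**Assumptions not in the documents.** Two-sided 5% level; shape of the log10 HBV DNA distribution; effect linear on the log hazard; constant response hazard reaching 80% by week 144, −ln(0.2)/144 = 0.0112 per week; exponential dropout of 15% by week 144, −ln(0.85)/144 = 0.0011 per week. Mean events in the simulations with no effect were about 150 of 200, or 127 of 170.

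**Step 1: information kept by a fixed two-group cut.** For a normal covariate cut at quantile q, the share kept is φ(z_q)²/[q(1−q)].

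| Case | Kept | Lost |
|---|---|---|
| Normal, median | 2/π = 0.637 | 36% |
| Normal, 30th percentile | 0.576 | 42% |
| Normal, 20th percentile | 0.490 | 51% |
| Uniform, median | 0.750 | 25% |
| Right-skewed (exponential), median | (ln 2)² = 0.480 | 52% |

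With a normal median split, 200 subjects do the work of about 200 × 0.637 = 127 in this test. More extreme cuts cost more: a normal cut at the 10th percentile keeps 0.342. More groups cost less: three equal groups lose about 21% and four about 14%, before the cost of extra degrees of freedom. In simulation, the median-split loss was 34–39% for normal, 25–27% for uniform and 39–44% for the skewed case.

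**Step 2: power at N=200, normal covariate, linear effect.** Two independent simulations (800 and 1,500 trials per setting) gave:

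| Log hazard ratio per SD (absolute) | Continuous | Median split |
|---|---|---|
| 0.15 | 44% | 29% |
| 0.20 | 67–68% | 50% |
| 0.25 | 86% | 66–68% |
| 0.30 | 95% | 80–81% |

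At 0.25 per SD, the uniform covariate gave 88% against 75%, and the skewed one 79% against 53%.

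**Step 3: false positives with no true effect (4,000 trials each at N=170 and N=200).**

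| Rule | Rejections at nominal 5% |
|---|---|
| Continuous score test | 5.0–5.7% |
| Fixed median cut | 4.7–5.0% |
| Best of 3 quartile cuts | 13% |
| Best of 5 sextile cuts | 18–19% |
| Best of 9 decile cuts | 26% |
| Best of all cuts, 25th–75th percentile | 29% |
| Best of all cuts, 10th–90th percentile | 43% |

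For the last two rows, the Miller–Siegmund approximation gives 31% and 49%, the same order. A fixed cut does not inflate the error rate. Only a search does.

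**The case against.** The case against making much of this is substantial, and most of it stands.

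- **Grouping is not forced.** A reader might infer that a log-rank test obliges the sponsor to cut HBV DNA. It does not: the test has a score form for a continuous covariate. The plan does not say which is meant, so the defect is an unstated form.
- **HBV DNA level is examined elsewhere.** A reader might infer that the trial as a whole loses this information. The Cox and logistic models both include HBV DNA level; if it is continuous there, only the univariable test loses anything. But their form is unstated too, and the Cox model takes its factors from the log-rank list, so continuous entry cannot be assumed.
- **The objective on viral titer at week 144 is served by the logistic model.** The time-to-response endpoint in SAP 5.3 names mutation patterns, not titre. The Protocol 1.2 remark concerns why studies differ on adefovir resistance, which a univariable test of viral load would not settle.
- **No cut search is planned.** Opportunity exists, but intent is not shown. The log-rank, Cox and Kaplan-Meier outputs are not marked for the annual reports, and no annual table or figure title groups response by baseline HBV DNA.
- **The power comparison assumes linearity.** The 64% is a squared correlation and works both ways: if the true effect were a step at the median, the continuous test would keep only about 64%.
- **Normality is assumed.** Entry at or above 200 IU/mL cuts off the lower tail, so a range is needed.
- **The mock tables may define groups.** A cut fixed there would answer the risk of a chosen cut, but not the loss of information.

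**Conclusion.** The concern holds as a gap in specification with a measurable cost. HBV DNA level has no groups, cut or functional form in the log-rank test, and no stated form in the Cox and logistic models.

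If it is split in two, the univariable time-to-response test loses about 36% of the information under normality and a median cut, or about 25–52% over median splits of the other shapes and normal cuts down to the 20th percentile. The example of 86% against 66–68% power rests on N=200, 0.25 per SD and a roughly linear effect.

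The 13–43% false-positive range applies only if someone searches for a cut. It is not an error rate of this plan, and a reader should not infer that the plan proposes a search. Nor do the documents support reading this as a threat to a main result: the analysis is exploratory, no hypothesis is tested, no alpha is attached, and the primary proportion at week 144 does not depend on it. This is a worthwhile minor improvement.

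**What to change.** In SAP 7.4.3:

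- Replace the grouped log-rank test for HBV DNA level with a score test of continuous log10 baseline HBV DNA in a one-factor Cox model.
- State that HBV DNA enters the multi-factor Cox and logistic models as continuous log10, and add a linearity check.
- Use groups only for display. Document the cut before the outcome data are examined or, at the latest, before final database lock.
- Close the same gap for compliance in the log-rank list. SAP 7.1 sets 80% and 120% limits for protocol deviations but does not link them to this test.

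The cost is a few lines of SAP wording, with no new data, visits or subjects. The price is the linearity assumption, since a true step effect would favour a grouped test; the linearity check is there to detect that.
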